## Introduction Page

1 \* Abbreviated Title:  
Microbiology Study

2 \* Full Title:  
Early Determination of Biofilm Formation on Orthopaedic Devices

3

\* Select Type of Submission:

IRB Application

Humanitarian Use Device (for FDA approved Indication & non-research purposes ONLY)

Emergency Use

Unsure if this proposal requires IRB review (Not Human Subject Research)

**Note: The Type of Submission cannot be changed after this application has been submitted for review.**

4 Original Version #:

ID: VIEW4DF8709A33C00  
Name: v2\_Introduction Page

**IMPORTANT NOTE:** All research team members (including PI) must have current CITI and HIPAA training completed.

ID: VIEW4DF85C16F2800  
Name: v2\_Research Team Information

## Resources

If this study is a collaborative UM/VA study, please clarify which resources are being used at each institution.

- 1 **\* Describe the time that the Principal Investigator will devote to conducting and completing the research:**  
PI will be involved in consenting and ongoing monitoring of data. Most of the sample collection and analysis will be conducted by other trained staff members and in the laboratory of Sub-Investigator ([name]).
- 2 **\* Describe the facilities where research procedures are conducted:**  
Shock Trauma Outpatient Clinic  
Lab of [name] (University of Maryland Dental School)
- 3 **\* Describe the availability of medical and/or psychological resources that subjects might need as a result of anticipated consequences of the human research:**  
Available through the outpatient clinic staff members. Patients will be referred to outside providers if needed.
- 4 **\* Describe the process to ensure that all persons assisting with the research are adequately informed about the protocol, the research procedures, and their duties and functions:**  
Patients will be given informed consent by a member of the research staff. They will then be allowed to ask any questions to the staff regarding the project prior to signing the consent document. They will be given a copy of the consent form as well.

ID: VIEW4DF83CB976400  
Name: v2\_Resources

## UM Coordinating Center

You indicated that UM is the Coordinating Center for this multi-site study.

**2.1** \*Describe the processes to ensure communication among sites.

Things to consider including in the communication plan:

- all sites have the most current version of the protocol, consent document, etc.
- all required approvals have been obtained at each site (including approval by the site's IRB of record).
- all modifications have been communicated to sites, and approved (including approval by the site's IRB of record) before the modification is implemented.
- all engaged participating sites will safeguard data as required by local information security policies.
- all local site investigators conduct the study appropriately.
- all non-compliance with the study protocol or applicable requirements will be reported in accordance with local policy.

This is not a true multi-center study. We are, however, coordinating the data collection efforts between the clinic staff and the laboratory of analysis.

**2.2** \*Describe the method for communicating to engaged participating sites including:

- reportable new information.
- problems.
- interim results.
- the closure of a study.

This is not a true multi-center study. We are, however, coordinating the data collection efforts between the clinic staff and the laboratory of analysis.

ID: VIEW4DF737D4C2800  
Name: v2\_UM Coordinating Center

## Funding Information

**1** \* Indicate who is funding the study:

- Federal
- Industry
- Department / Division / Internal**
- Foundation

- Private
- State Agency

2 \* What portion of the research is being funded? (Choose all that apply)

- Drug
- Device
- Staff
- Participant Compensation
- Procedures
- Other

3 Please discuss any additional information regarding funding below:

ID: VIEW4DF85DF452400  
Name: v2\_Funding Information

## Research Protocol

1 \* Do you have a research protocol to upload?

- Yes
- No, I do not have a research protocol and will use the CICERO application to enter my study information

2 If Yes, upload the research protocol:

Name	Created	Modified Date
------	---------	---------------

There are no items to display

ID: VIEW4E00563F8D000  
Name: v2\_Research Protocol

## Risk Level

**What is the risk level of your study? (Ultimately, the IRB will determine the appropriate risk level and your designation is subject to change.)**

\* Choose One:

- Minimal - The probability & magnitude of harm/discomfort anticipated in the research are not greater in and of themselves than those ordinarily encountered in daily life or during the performance of routine physical or psychological examinations/tests.
- Greater Than Minimal - Does not meet the definition of Minimal Risk.

ID: VIEW4E02805225800  
Name: v2\_Risk Level

## Type of Research

1 \* Indicate **ALL** of the types of research procedures involved in this study (Choose all that apply):

- Use of unapproved drug(s)/biologic(s) or approved drug(s)/biologic(s) whose use is specified in the protocol.
- Evaluation of food(s) or dietary supplement(s) to diagnose, cure, treat, or mitigate a disease or condition.
- Use of device(s) whose use is specified in the protocol
- Psychological/Behavioral/Educational Method or Procedure (i.e., survey, questionnaires, interviews, focus groups, educational tests).

- Sample (Specimen) Collection and/or Analysis (including genetic analysis).**
- Data Collection or Record Review (i.e., chart review, datasets, secondary data analysis).**
- None of the above.

2 \* Is this study a clinical trial OR will this study be registered at ClinicalTrials.gov?

A clinical trial is a research study in which one or more human subjects are prospectively assigned to one or more interventions (which may include placebo or other control) to evaluate the effects of those interventions on health-related biomedical or behavioral outcomes.

Yes  No

ID: VIEW4E0280569E000  
Name: v2\_Type of Research

## Lay Summary

1 \* Provide a summary of the background and purpose of the study in language that can be understood by a person without a medical degree.

Surgical site infection in the orthopaedic surgery population is a significant public health issue. Wound infections result in both increased length of hospital stay and total cost of care.

Surgical site infection (SSI) is the most common preventable adverse outcome after a major operation. The economic costs to the US healthcare system are enormous estimated to be in excess of \$1.8 billion per year. For patients who develop an SSI, the cost may be even higher with length of stay and risk of death doubled. Thus the benefits of any intervention decreasing the risk of SSI are very tangible.

A biofilm is a layer of bacteria that adheres to a surface; in Orthopaedics, this often means adherence to implanted metal after fracture surgery. The test that has been designed by one of the investigators on the study has been shown in an animal model to detect the formation of a biofilm up to 1 month prior to clinical detection. Having a blood assay such as this would allow earlier antibiotics and potentially prevent the need for further surgeries to remove metal implants and clean out the biofilm.

ID: VIEW4E02805CF7000  
Name: v2\_Lay Summary

## Justification, Objective, & Research Design

**If you uploaded a separate research protocol document in the 'Research Protocol' page, cite the applicable section and page numbers from that document in the answer boxes below.**

1 \* Describe the purpose, specific aims, or objectives of this research. State the hypothesis to be tested:

To determine if a new assay to detect early biofilm colonization can be validated in acute postoperative wound infections in orthopaedic trauma patients who have sustained high energy open/closed lower extremity fractures. This would potentially help decrease the amount of surgical interventions needed for infections as it could allow for early intervention and antibiotics.

2 \* Discuss the research design including but not limited to such issues as: probability of group assignment, potential for subject to be randomized to placebo group, use of control subjects, etc.:

A prospective trial conducted at Shock Trauma of patients between 18 years of age and older who have sustained a fracture with metal implanted. We will be collecting between 1-3 routine blood draws for the purpose of laboratory analysis to assess biofilm growth. Patients may be infected or non-infected at the time of blood draw; they will be selected at random for purposes of this study. All patients will be followed as standard of care by their treating physician for all their follow up visits.

3 \* Describe the relevant prior experience and gaps in current knowledge. Describe any relevant preliminary data:

Surgical site infection in the orthopaedic surgery population is a significant public health issue. Wound infections result in both increased length of hospital stay and total cost of care. Specifically, a biofilm assay would help identify early infection in patients and potentially reduce the need for re-operations for infections as it would allow early antibiotic delivery to the affected areas. Our bacteria of focus would be Methicillin-resistant Staphylococcus aureus (MRSA), as this is one of the most predominant organisms in orthopaedic surgical site infections, but can be included to other pathogens causing surgical site infections.

4 \* Provide the scientific or scholarly background, rationale, and significance of the research and how it will add to existing knowledge:

Surgical site infection in the orthopaedic surgery population is a significant public health issue. Wound infections result in both increased length of hospital stay and total cost of care. Specifically, a biofilm assay would help identify early infection in patients and potentially reduce the need for re-operations for infections as it would allow early antibiotic delivery to the affected areas. Our bacteria of focus would be Methicillin-resistant Staphylococcus aureus (MRSA), as this is one of the most predominant organisms in orthopaedic surgical site infections, but can be included to other pathogens causing surgical site infections.

ID: VIEW4E02805EA0C00  
Name: v2\_Justification, Objective, & Research Design

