## Study Procedures

**If you uploaded a separate research protocol document in the 'Research Protocol' page, cite the applicable section and page numbers from that document in the answer boxes below. (If this study is a collaborative UM/VA study please list each procedure that is being conducted and the locations where it is being conducted.)**

1 \* Describe all procedures being performed for research purposes only (these procedures would not be done if individuals were not in the study) and when they are performed, including procedures being performed to monitor subjects for safety or to minimize risks:

Patients will be identified at random in the orthopaedic trauma clinic and current admitted patients who have been diagnosed with an infection. Once eligibility has been confirmed, the informed consent process will be completed by the Research Coordinator and the attending surgeon. Patients will be approached about potential participation in the study as soon as is feasible following determination of eligibility.

Once consented into the study, baseline data regarding participant characteristics, injury characteristics, fracture classification and medical history/co-morbidities will be collected. Characteristics about hospital course and treatment received will also be collected (i.e. blood culture results, antibiotic usage, etc).

At each follow up visit, participants will undergo a clinical evaluation by the treating surgeon as part of standard of care following any surgical procedure and will be interviewed by the research coordinator. Blood draws will be taken at the initial and each subsequent visit and will be analyzed in the laboratory of one of the investigators in the study. If the patient is currently infected currently, or become infected at any point in the future, additional blood draws may be taken, at a maximum of 10 draws, over the period of two years from the clinical diagnosis of infection. The amount of blood that is drawn will not exceed 50 ml or 3 ml per kg in a 8 week period, and collection may not occur more frequently than 2 times per week.

Finally, we would prospectively correlate the laboratory findings with clinical findings by searching the patients' medical records to find outcomes such as a biofilm formation.

2 \* Describe all procedures already being performed for diagnostic or treatment purposes (if not applicable to the study, enter "N/A"):

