## Sample Size and Data Analysis

**If you uploaded a separate research protocol document in the 'Research Protocol' page, cite the applicable section and page numbers from that document in the answer boxes below.**

1 \* Provide the rationale and sample size calculations for the proposed target population:

In order to validate the designed test, we hypothesize needing a large study to determine if it is effective in a human model. Additionally, we will follow out the patients to determine if some become infected (the primary outcome of the study that we are trying to ultimately be able to predict. We anticipate 1000-1200 patients enrolled in this study).

2 \* Provide the plan for data analysis. Include in the description the types of comparisons that are planned (e.g., comparison of means, comparison of proportions, regressions, analysis of variance, etc.), which is the primary comparison/analysis, and how the analyses proposed will relate to the primary purposes of the study:

We will describe the population in terms of general descriptive statistics for age, injury, surgery and outcome. We will use t-testing and other statistical analysis as appropriate.

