## Prospective Samples

You indicated that the study involves collection of prospective samples (specimens).

1 \* What type of sample will be collected? (Check all that apply)

Blood  
 Bone Marrow Aspirate/Biopsy  
 Cerebrospinal Fluid  
 Saliva  
 Skin  
 Sputum  
 Stool  
 Tissue  
 Tumor  
 Urine  
 Other

1.1 If Other, specify:

2 For blood draws, specify the amount drawn, in teaspoons, at each visit and across the course of the subject's entire participation time:

Blood draws are routinely taken throughout a patient's follow-up to monitor their health. We plan to take up to three blood draws, with the use of an indwelling catheter when available, to culture for research purposes during their hospitalization for diagnosed surgical site infection.

Patients will be identified at random in the orthopaedic trauma clinic and current admitted patients who have been diagnosed with an infection. Once eligibility has been confirmed, the informed consent process will be completed by the Research Coordinator and the attending surgeon. Patients will be approached about potential participation in the study as soon as is feasible following determination of eligibility.

Once consented into the study, baseline data regarding participant characteristics, injury characteristics, fracture classification and medical history/co-morbidities will be collected. Characteristics about hospital course and treatment received will also be collected (i.e. blood culture results, antibiotic usage, etc).

At each follow up visit, participants will undergo a clinical evaluation by the treating surgeon as part of standard of care following any surgical procedure and will be interviewed by the research coordinator. Blood draws will be taken at the initial and each subsequent visit and will be analyzed in the laboratory of one of the investigators in the study. If the patient is currently infected currently, or become infected at any point in the future, additional blood draws may be taken, at a maximum of 10 draws, over the period of two years from the clinical diagnosis of infection. The amount of blood that is drawn will not exceed 50 ml or 3 ml per kg in a 8 week period, and collection may not occur more frequently than 2 times per week.

Finally, we would prospectively correlate the laboratory findings with clinical findings by searching the patients' medical records to find outcomes such as a biofilm formation.

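### The analysis plan sets no at-risk group and no draw-timing rule, so it permits a pooled infected-versus-non-infected test that could not by itself show detection before diagnosis

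*Combined protocol and SAP*

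**What the plan says.** **Purpose.** The Lay Summary cites an animal model in which the assay found biofilm up to one month before clinical detection. Study Procedures, item 2, places the assay ahead of any current testing. Sample Size and Data Analysis, item 1, gives the outcome: "we will follow out the patients to determine if some become infected (the primary outcome of the study". The same item opens with a validation aim ("In order to validate the designed test"), and the objective in the design section is validation in acute postoperative wound infections.

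**Who is sampled.** The design section states: "Patients may be infected or non-infected at the time of blood draw; they will be selected at random for purposes of this study". Eligibility admits inpatients with a known infection and patients admitted from clinic because of infection. Recruitment lists three groups: clinic follow-up patients, patients admitted directly from clinic, and current patients with a diagnosed infection.

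**Which draws.** The design section gives 1-3 routine draws. Study Procedures and Prospective Samples call for draws at the initial and every later visit. For infected patients both add that "additional blood draws may be taken, at a maximum of 10 draws, over the period of two years from the clinical diagnosis of infection". Prospective Samples also plans up to three draws "to culture for research purposes during their hospitalization for diagnosed surgical site infection".

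**Analysis.** After descriptive statistics, the analysis item says only: "We will use t-testing and other statistical analysis as appropriate". The nearest other text is in Study Procedures: "we would prospectively correlate the laboratory findings with clinical findings". The Research Protocol page lists no uploaded protocol that might say more.

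**The concern.** A patient whose infection is already diagnosed cannot become a new case of it, and a draw taken after diagnosis cannot show detection before diagnosis. Both kinds of data enter the study, and nothing in the plan keeps them out of the early-detection analysis. Excluding patients infected at enrolment would not be enough, because a patient who becomes infected during follow-up can also contribute post-diagnosis draws.

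Two questions are left mixed: whether the assay distinguishes established infection from none, and whether it changes before the clinician knows. A positive pooled result could come wholly from the first, and a real early signal could be diluted by later draws. The documents fix neither the direction nor the size. The mouse study in Supporting Literature contrasts early with chronic biofilm, not before with after diagnosis, so it suggests only that stage of infection may matter.

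**Working it through.** **The plan's own figure.** The anticipated 1000-1200 patients comes with no error rate, power, effect size, infection rate or share already infected. It cannot be reproduced, and the point does not depend on it.

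**Step 1: purpose against plan.** An analysis of becoming infected needs (a) patients undiagnosed at the draw, (b) draws taken before diagnosis, and (c) a definition of case and non-case over a stated time. The analysis item gives none of these. Correlating laboratory with clinical findings does not supply them.

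**Step 2: what a pooled test could do.** N = 1200 is from Participant Selection. Everything else is assumed: 120 patients ever infected, 1080 never infected, one value per patient with SD 1, a two-sided 5% t-test, a signal of 0.5 SD, and a share f of the infected already diagnosed at the draw. With signal only after diagnosis, the mean shift in the pooled infected group is 0.5f. With signal only before, it is 0.5(1 − f). In the normal approximation, power is Φ(shift/SE − 1.96).

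- Pooled SE = √(1/120 + 1/1080) = 0.0962.
- f = 0.5, signal on one side only: shift 0.25; 0.25/0.0962 = 2.60; Φ(0.64) = 0.74.
- Pre-diagnosis cases only (60 against 1080): SE = √(1/60 + 1/1080) = 0.1326; 0.5/0.1326 = 3.77; Φ(1.81) = 0.965.
- Signal in both: 0.5/0.0962 = 5.20; Φ(3.24) = 0.999.

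Simulation (10,000 runs) agrees with these approximations. The proportion of studies significant was:

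| Already diagnosed (f) | Signal only after: pooled | Signal only after: pre-diagnosis cases only | Signal only before: pooled | Signal only before: pre-diagnosis cases only |
|---|---|---|---|---|
| 25% | 0.247 | 0.049 | 0.975 | 0.995 |
| 50% | 0.732 | 0.047 | 0.739 | 0.965 |
| 75% | 0.976 | 0.051 | 0.257 | 0.780 |

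At f = 50% with 60 or 240 infected patients, the pooled test is significant in 0.470 or 0.935 of studies when the signal is only after diagnosis. When it is only before, pooled power is 0.471 or 0.931, against 0.772 or 1.000 with pre-diagnosis cases only.

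With signal in both, pooling costs no power (0.999 against 0.965). A significant result is still uninformative about timing, because at f = 50% it also appears in about 73% of studies when there is no pre-diagnosis signal.

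**Step 3: share of draws after diagnosis.** With k draws before and m after, the share is m/(m + k). If 10 later draws are additional to the earlier ones, it is 10/11 = 91% for k = 1 and 10/13 = 77% for k = 3. For k = 6, which draws at every visit would allow, it is 10/16 = 62.5%. With no later draw it is 0%, and for a patient diagnosed before enrolment it is 100%. The draw statements do not agree on k or m, so the share cannot be fixed.

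**The case against.** **The pooled test is an inference.** The analysis item names no groups. A primary outcome of becoming infected already implies patients at risk, and the intended correlation is described as prospective. A reader might infer from the mixed enrolment that the plan pools everyone; the documents do not say so. What stands is that nothing rules pooling out and the choice is left until after the data are seen.

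**Known infections belong in a validation study.** This stands. The stated objective is validation in acute postoperative infections, and comparing infected with non-infected patients is a legitimate step towards it. A reader might infer that these patients should not have been enrolled, and the documents do not support that. They answer a different question and need their own analysis set.

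**The signal may be present both before and after diagnosis.** Then pooling dilutes nothing, as Step 2 shows. This limits the claim about lost power but does not make a pooled result evidence of early detection.

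**Random selection.** A reader might infer that every mention of randomness contradicts the recruitment groups. The sentence in Study Procedures and Prospective Samples ("Patients will be identified at random in the orthopaedic trauma clinic and current admitted patients who have been diagnosed with an infection") can be read as applying randomness to clinic patients only. The blanket statement in the design section is the one that clearly does not fit, since one recruitment group is defined by a diagnosed infection.

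**Conclusion.** The concern holds as an omission in the analysis plan and should be fixed. The plan does not separate already-diagnosed patients or post-diagnosis draws from patients still at risk. The comparison it leaves open could not by itself show detection before diagnosis.

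That conclusion rests on the text alone. The percentages are illustrations, resting on assumed effect size, case counts and share already diagnosed.

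Two stronger readings should be avoided. A reader might infer that the collected data could never support an early-detection analysis. Serial draws, follow-up and a Diagnosis of Infection Form (listed under Additional Documents, fields not shown) suggest they might. A reader might also take 77%-91% as a ceiling on the post-diagnosis share of draws. It holds only for 1-3 earlier draws, and the documents also allow a draw at every visit.

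**What to change.** **In Sample Size and Data Analysis, item 2:**

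- Make the primary early-detection analysis the patients with no clinical diagnosis of infection at the draw, using pre-diagnosis draws only.
- Count infections diagnosed afterwards as cases, and report results by time from draw to diagnosis.
- Count a draw as a non-case for a window only if the patient is known to be undiagnosed through it; otherwise censor it.
- Use one index draw per patient, or a method that allows for repeated draws.
- Analyse known infections and all post-diagnosis draws separately, as an established-infection validation set. This serves the stated objective.
- State which set holds draws taken during an admission for suspected infection. Cultures are sent to confirm such cases, so diagnosis may be pending at the draw.
- Take no predictive values from the combined sample, since they would reflect the recruitment mix.

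**Elsewhere:** reconcile the design section's statement on random selection with the three recruitment groups, and reconcile the statements on number and timing of draws.

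**Cost.** These are wording changes made before analysis. Assay results are withheld from treating surgeons and do not affect care, so the change of analysis requires no new procedure. Draw and diagnosis dates must be obtainable from the form or the medical record. There will be fewer primary cases and wider intervals: for an assumed 80% sensitivity with 60 cases (48/60), the Wilson 95% interval is 68% to 88%. Some patients will be censored, because follow-up is by routine visits with no fixed duration, supplemented by telephone for those who do not return (Waiver/Alteration of Authorization).
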